Primary Objectives	To evaluate the antithrombotic efficacy of prophylactic xisomab 3G3 treatment in cancer patients with a central venous catheter.

Secondary Objectives	To determine the safety and tolerability of prophylactic xisomab 3G3 treatment as measured by the incidence and severity of adverse events in cancer patients with a central venous catheter.
Exploratory Objective	Assessment of participant coagulation profiles, and the incidence of line occlusion requiring medical interventions to obtain patency.
Primary Endpoints	The number of participants with catheter-associated thrombosis, as defined by the total incidence of symptomatic and asymptomatic thrombosis, and thrombotic occlusion leading to device failure (start: administration of xisomab; end: Day 18)
Secondary Endpoints	The number of subjects with treatment-related adverse events (TRAEs) and treatment-emergent adverse events (TEAEs) will be summarized using frequency counts (start: time of consent, end: Day 60)
Exploratory Endpoints	Quantification of coagulation parameters and assessment of catheter occlusion (start: pre-dose, end: Day 18 [i.e., post-dose]): 
 
a. Activated partial thromboplastin time (aPTT)
 
b. Pharmacokinetic (PK) evaluation
 
c. Time to symptomatic catheter-associated thrombosis
 
d. Proportion of participants with a catheter occlusion requiring medical intervention
 

Number of Participants	
Duration of Therapy	1 day
Duration of Follow Up	60 days [post catheter placement]
Key Inclusion Criteria	
 
• Men and women, aged <math>\geq</math> 18 years and members of all races and ethnic groups will be included.
 
• Participants with any solid tumor malignancy that will undergo insertion of a central venous catheter (PICC or indwelling subclavian vein central venous catheter) as part of planned cancer-directed therapy per institutional standards
 
• Able to wait 1 day post-study drug infusion before receiving cancer-directed therapy.
 
• ECOG performance status <math>\leq</math> 2
 
• Expected life expectancy of <math>>6</math> months
 
• At time of enrollment, must have adequate platelet count (<math>>100 \times 10^9/L</math>)
 

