## 5. TREATMENT PLAN

### 5.1 DOSAGE AND ADMINISTRATION

Treatment will be administered on an *out-patient* basis. Reported adverse events and potential risks are described in Section 7.4, Adverse Event List.

Regimen Description			
Agent	Dose	Route**	Schedule
Xisomab 3G3	2 mg/kg	IV (via catheter)	Single dose administered within 48 hours of catheter placement ( $\pm$ 2 days).

\*\*Study drug should be administered as a slow bolus (approximately 1 minute).

Enrolled participants will receive a single fixed dose of xisomab 3G3 (2 mg/kg) through a peripheral IV or the inserted catheter within 48 hours of catheter placement (i.e.  $\pm$  2 days). If Xisomab 3G3 is administered prior to D1 catheter placement, eligibility must be confirmed prior to study drug administration. Participants will be monitored for at least 1 hour on the day of xisomab 3G3 administration for adverse events. Participants not receiving study drug or catheter placement as scheduled, may be rescheduled if within allowable screening window (i.e., no more than 28 days from consent). Participants receiving study drug but have a delay in placement of the catheter beyond 48 hours from time of xisomab administration, will not be considered evaluable for efficacy analysis (per Section 8.1), but will be followed for xisomab 3G3-associated toxicities (per Section 6.7).

Two (2) days after participants receive study drug they may proceed to undergo planned anticancer therapy per standard of care. Administration of planned cancer-directed therapy may not occur earlier than 2 days from time of giving study drug. The type(s) and frequency of administration of anticancer drug(s) comprising the participants' anticancer treatment regimen is at the discretion of treating physician and should be recorded in the CRF.

Consistent with institutional standards, participants may at any time during the study receive a standard of care workup with an ultrasound if they develop symptoms the investigator (or treating physician) believes to be suggestive of CAT, including arm pain and swelling or erythema in the same arm as the catheter. In such cases, the participant may receive antithrombotic therapy, at the discretion of their treating physician, per institutional guidelines.

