#### **6.1.8 ULTRASOUND**

Per institutional standards, catheters are evaluated for possible CAT via venous duplex ultrasonography 14 ( $\pm 4$ ) days from time of catheter placement (which will be  $\pm 2$  days from administration of study agent). Venous duplex ultrasonography to occur as part of EOT visit, prior to provider visit. Assessment will include compression imaging of all the accessible portions of the internal jugular, innominate, subclavian, axillary, cephalic and basilic veins, as well as color Doppler of the internal jugular, subclavian and axillary veins. VTE will be diagnosed based on non-compressibility of a vein segment and/or abnormal color Doppler patterns. Whether the presence of CAT in a participant is symptomatic or asymptomatic at time of ultrasound evaluation will be noted in CRF as part of assessment.

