## 6.9 SCHEDULE OF EVENTS

Visit Days*	Screening**	On-Study Treatment	End of Treatment Visit Day 14 ( $\pm 4$ days)	Follow-Up Day 60 ( $\pm 4$ days)
	Days -28 to -3	Day 1		
Informed consent	X			
Inclusion/exclusion criteria	X			
Catheter placement A		X		
Xisomab 3G3		X		
Medical history	X			
Medication history	X			
Physical Examination C	X	X G	X	
Radiographic Imaging		Per investigator's discretion, as clinically indicated		
Ultrasound D			X	
Hematology	X			
Biochemistry	X			
Coagulation	X		X	
Pregnancy test E	X			
AE assessment and Conmeds B,F	X	X	X	X
Research blood draw/Assessment for Immunogenicity H	X	X	X	
Electrocardiogram I	X	As clinically indicated		

\* Ideally the clinic visit and all the study requirements should be performed as indicated.

\*\* Enrolled participants will receive a single fixed dose of xisomab 3G3 (2 mg/kg) through a peripheral IV or the inserted catheter within 48 hours of catheter placement (i.e.  $\pm 2$  days). If Xisomab 3G3 is administered prior to D1 catheter placement, eligibility must be confirmed prior to study drug administration.

A Placement of the catheter in participants will be performed according to institutional guidelines. Ultrasound may be used to guide the placement of the catheter, and may include use of local anesthetic.

B For concomitant medications – enter new medications started during the trial through the end of treatment visit.

C All physical exams will include assessing vital signs, weight and ECOG performance status.

D Per institutional standards, study participants will be evaluated for CAT via planned ultrasound 14  $\pm 4$  days after catheter insertion. Additional ultrasound evaluations may occur at any time during the study based on treating physician and PI discretion; however, only ultrasounds performed within 18 days from catheter placement will be included when computing CAT incidence. Ultrasound to occur as part of EOT, prior to provider visit.

E For women of reproductive potential, a serum pregnancy test should be performed within 3 days prior to first dose of trial treatment. Serum pregnancy test should be performed by the local study site laboratory per institutional guidelines, and repeated if required.

Visit Days*	Screening**	On-Study Treatment	End of Treatment Visit Day 14 ( $\pm 4$ days)	Follow-Up Day 60 ( $\pm 4$ days)

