### 8.1 ANALYSIS POPULATIONS

An intent to treat (ITT) analysis set consists of all participants who consent and enroll in the trial regardless of whether they are exposed to the study drug. An efficacy analysis set consists of participants who have placement of a catheter, receive xisomab 3G3 within 48 hours of catheter placement, and have at least one CAT assessment (i.e., ultrasound and physical exam) by Day 18 of the study. A safety analysis set consists of all participants who are exposed to the single dose of study drug.

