#### 8.2.2 ANALYSIS OF PRIMARY ENDPOINT

Using the efficacy analysis set, the incidence of ultrasound-detected CAT (including both symptomatic and asymptomatic clots) in the first 18 days after catheter insertion will be assessed and reported with a 95% CI. CAT incidence will also be separately estimated for each general catheter type (i.e., PICC vs. indwelling port).

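### Section 8.1 asks for a physical exam as well as an ultrasound for the efficacy set, so a participant with a valid scan could be excluded from an analysis that uses only the scan (minor)

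*Combined protocol and SAP*

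**What the plan says.** Section 8.1 sets three conditions for the efficacy set: a catheter is placed, xisomab 3G3 is given within 48 hours of placement, and participants "have at least one CAT assessment (i.e., ultrasound and physical exam) by Day 18 of the study". The parenthesis defines the assessment and names both parts.

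Section 8.2.2 then specifies the primary analysis: "Using the efficacy analysis set, the incidence of ultrasound-detected CAT (including both symptomatic and asymptomatic clots) in the first 18 days after catheter insertion".

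The places that settle whether a participant has an event refer to imaging:

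- Section 6.1.8: "VTE will be diagnosed based on non-compressibility of a vein segment and/or abnormal color Doppler patterns".
- Section 6.9, footnote D: "only ultrasounds performed within 18 days from catheter placement will be included when computing CAT incidence".

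The same footnote fixes the order at the end of treatment (EOT) visit: "Ultrasound to occur as part of EOT, prior to provider visit". Outside that visit, Section 5.1 says "participants may at any time during the study receive a standard of care workup with an ultrasound if they develop symptoms" suggestive of CAT. Section 6.7 ends follow-up at 60 days, at the start of off-study anticoagulation, or at death, whichever comes first.

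Three other places bear on the point. Sections 2.1 and 6.5 describe the scan as accompanied by a history and physical exam. Section 8.4 says that available data are used where possible, that nothing is imputed, and that exclusions are reported with reasons. The Synopsis endpoint is wider than ultrasound, since it also lists "thrombotic occlusion leading to device failure".

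**The concern.** The efficacy set asks for something that the analysed outcome does not use. Section 8.2.2 counts symptomatic and asymptomatic clots alike, so the exam can change the label on an event but not whether there is one. An inclusion rule that goes beyond what the outcome needs can remove participants whose outcome is already known.

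There are two ways a scan could lack a qualifying exam by Day 18:

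1. The scan comes before the provider visit, and that visit is missed or falls after Day 18.
2. A participant has an early scan for symptoms, starts anticoagulation, and reaches the end of follow-up under Section 6.7 before the Day 14 exam.

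If inclusion then depended on the scan result, the primary estimate would be biased. With about 48 evaluable participants and no concurrent control, each exclusion shifts the estimate by roughly one percentage point. The decision would also be taken in an open trial with the result in view.

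**Working it through.** **The plan's own figure.** Inputs from Section 8.3.1: historical rate p0 = 0.60, a 20-point reduction (p1 = 0.40), two-sided alpha 0.05, power 80%, 4% ineligible for efficacy. The one-sample normal approximation is

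n = [z(0.975)·√(p0(1−p0)) + z(0.80)·√(p1(1−p1))]² / (p0−p1)²

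= 0.24 × (1.960 + 0.842)² / 0.04 = 47.1, rounded up to 48. Then 48/0.96 = 50, which reproduces the stated size. The 4% allowance covers 50 − 48 = 2 participants for all reasons together.

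**Set against outcome.**

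| Place | What it decides | Exam needed? |
|---|---|---|
| 8.1 | Who is in the efficacy set | Yes, as written |
| 8.2.2 | What is analysed | No |
| 6.1.8 | How thrombosis is diagnosed | No |
| 6.9, footnote D | Which scans count | No |

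Section 8.1 does not say which exam qualifies. Exams are also scheduled at screening and around dosing (6.1.4, 6.9), and a clinician may examine the participant at a symptomatic workup. Two analysts could therefore build different sets from the same data.

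**One exclusion.** The counts are assumed; limits are exact (Clopper-Pearson) 95%.

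- No exclusion: 22/48 = 45.8% (31.4 to 60.8).
- One scan-positive lost: 21/47 = 44.7% (30.2 to 59.9).
- One scan-negative lost: 22/47 = 46.8% (32.1 to 61.9).

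The move of the upper limit across 60% is particular to this count. Over starting counts of 10 to 34 out of 48, 22 is the only one at which losing one positive does this. Near the design alternative, 19/48 = 39.6% has an upper limit of 54.7%; 18/47 = 38.3% has 53.6%.

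**Range of one-sided losses.** The documents give no rate of scans without exams, so the share q is an assumption. If only positives are lost, the apparent rate is p(1−q)/(1−pq). If only negatives are lost, it is p/(1−(1−p)q).

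| q | True 60%, positives lost | True 60%, negatives lost | True 40%, positives lost | True 40%, negatives lost |
|---|---|---|---|---|
| 0 | 60.0% | 60.0% | 40.0% | 40.0% |
| 5% | 58.8% | 61.2% | 38.8% | 41.2% |
| 10% | 57.4% | 62.5% | 37.5% | 42.6% |
| 20% | 54.5% | 65.2% | 34.8% | 45.5% |

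**If the result were tested against 60%.** An exact lower-tail rule at 0.025 with n = 48 rejects at 21 or fewer events and has a true error of 1.7%. Simulating the loss of positives only (400,000 trials, rule recomputed for the remaining n) gives about 2.8%, 3.8% and 7.5% at q = 5%, 10% and 20%. Part of the first step is discreteness: with n = 47 and no bias the rule also rejects at 21 or fewer, with error 2.4%. Section 8.2.2 states no such test, so these figures are only a guide to sensitivity.

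**The case against.** The strongest reply is that scan and exam form one assessment. Sections 2.1 and 6.5 pair them, 6.1.8 places the scan inside the EOT visit, and the parenthesis in 8.1 may only restate that. A symptomatic scan is prompted by a clinician's suspicion, and the arm signs in Section 5.1 are those that 6.1.4 lists for the CAT exam, so some examination is likely. Sections 5.3.3 and 6.6.1 also point to more clinician contact after a positive finding or early termination. Section 8.4 favours using available data and would make any exclusion visible.

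Much of this stands, and it makes the case uncommon. It does not settle it. The pairing describes intended conduct; a set definition must also say what happens when the pairing fails. Section 8.4 does not override the set named in 8.2.2, and it also allows a participant's data to be excluded entirely or partially in consultation with the biostatistician.

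A reader might infer four stronger things that the documents do not support:

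- *Participants with valid scans are dropped.* No section says so, and 8.1 does not require the exam to follow the scan or to take place at a study visit.
- *The losses are mainly events, so CAT is underestimated.* That is plausible on the symptomatic route, but nothing establishes it overall. A well participant with a negative scan could equally skip the provider visit.
- *One exclusion would change the trial's conclusion.* This rests on a single count and on a 60% boundary that 8.2.2 does not set.
- *The endpoint is ultrasound alone throughout.* That fits 8.2.2, but the Synopsis adds device failure from thrombotic occlusion. Nothing in that addition makes an exam necessary either.

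**Conclusion.** The mismatch is real: the exam condition in 8.1 is stricter than the outcome analysed in 8.2.2 requires, and a literal reading could exclude a participant with a known result. The bias could run either way, depending on whether those excluded are scan-positive or scan-negative. One exclusion moves the estimate by about one percentage point at the illustrative count. The overall effect is probably small, and it is zero if every scan has a qualifying exam. These sizes rest on assumed counts and assumed loss rates, because the documents give none. Severity: minor. It is worth correcting because the wording leaves a choice about the primary analysis set to be made after the scan result is known.

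**What to change.** In Section 8.1, replace the parenthesis so that the CAT assessment means an ultrasound only, performed within 18 days of catheter placement. Inclusion then uses the same window as footnote D of Section 6.9. Add that any positive scan in that window counts as an event whether or not an exam is recorded. Keep the exam as the source of the symptomatic or asymptomatic label, report the label as missing where there was no exam, and report the number of scans without an exam.

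The cost is one phrase and a sentence or two. The planned size stays at 48 evaluable and 50 enrolled, and no visit or procedure changes.

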### 8.2 DESCRIPTION OF STATISTICAL METHODS

#### 8.2.1 GENERAL APPROACH

This is a single arm phase II trial to assess the efficacy of xisomab 3G3 in reducing the incidence of CAT over 18 days after catheter placement. This study will enroll 50 patients with non-leukemic cancer who are to undergo placement of a central venous catheter and who can wait 2 days from xisomab infusion before initiating antineoplastic therapy.

#### 8.2.2 ANALYSIS OF PRIMARY ENDPOINT

Using the efficacy analysis set, the incidence of ultrasound-detected CAT (including both symptomatic and asymptomatic clots) in the first 18 days after catheter insertion will be assessed and reported with a 95% CI. CAT incidence will also be separately estimated for each general catheter type (i.e., PICC vs. indwelling port).

#### 8.2.3 ANALYSIS OF THE SECONDARY ENDPOINTS

The incidence of major or clinically relevant non-major bleeding (defined in Section 6.1.9.1), along with 95% CI, will be assessed using the safety analysis set. The proportion of safety set participants with these bleeding events will also be separately estimated for each catheter type.

The incidence of xisomab 3G3-associated toxicities will be assessed using the safety analysis set. Descriptive statistics of safety will be presented using CTCAE v5.0. All on-study AEs (from time of consent), treatment-related AEx (from time of xisomab infusion), SAEs, and treatment-related SAEs will be tabulated using worst grade per NCI CTCAE v5.0 criteria by system organ class and preferred term. On-study abnormal lab parameters including hematology, chemistry, liver function, and renal function will be summarized using worst grade NCI CTCAE v5.0 criteria.

#### 8.2.4 ANALYSIS OF THE EXPLORATORY ENDPOINTS

Descriptive statistics will be used to present results of coagulation measures (i.e., platelet count, PT/INR, and aPTT), drug PK, and incidence of catheter occlusion requiring medical therapy (specifically, local administration of tPA). The proportion of participants with symptomatic thrombosis by Day 18 and the median (and range) time from xisomab infusion to clot symptoms

will be reported for those (expected few) participants with symptomatic CAT. All exploratory endpoints will additionally be analyzed within each catheter type (i.e., PICC vs. indwelling central venous catheter).

### 8.3 SAMPLE SIZE, POWER, ACCRUAL RATE AND STUDY DURATION

#### 8.3.1 SAMPLE SIZE AND POWER

Based on the central venous catheter thrombosis rates and other parameters (e.g., population type, thrombosis evaluation period) in prior studies, the sample size calculation makes the assumption of a 60% incidence of ultrasound-confirmed CAT (i.e., both symptomatic and asymptomatic) over 18 days post- catheter placement in cancer patients not treated with xisomab. A sample size of 50 participants, accounting for a 4% efficacy ineligibility rate, is sufficient to provide 80% power to detect a 20 percentage point reduction in the incidence of CAT at a two-sided  $\alpha$  of 0.05.

### 8.4 HANDLING OF MISSING DATA

Every attempt will be made to obtain data at the defined time points as described in the primary and secondary endpoint descriptions (section 2.2) and the schedule of events (section 6.9). If the data are not sufficient to analyze specific endpoints, the participant's data may be excluded entirely or partially, depending on the specific endpoints in question and in consultation with the biostatistician. No missing data will be imputed. Whenever possible, all available data will be included in the analysis. A sample size for each analysis will be clearly stated along with the reason for exclusion, if any participant is excluded from the analysis due to missing data.

## 9. CLINICAL MONITORING

### 9.1 OHSU KNIGHT CANCER INSTITUTE DATA & SAFETY MONITORING PLAN

This study is under the oversight of the Knight Cancer Institute's Data Safety and Monitoring Committee (DSMC) as described in the Knight's institutional Data and Safety Monitoring Plan (DSMP). The Knight DSMP outlines the elements required to ensure the safety of clinical trial participants, the accuracy and integrity of the data and the appropriate modification of cancer-related clinical trials for which significant benefits or risks have been discovered or when the clinical trial cannot be successfully concluded. The Knight DSMP also describes the methods and procedures for ensuring adequate oversight of cancer-related research at OHSU.

As described in the Knight DSMP, regardless of a trial's risk level and any specific Knight oversight in place, the Investigator is singularly responsible for overseeing every aspect of the design, conduct, and final analysis of his/her investigation.

The Knight DSMC reviews and monitors study progress, toxicity, safety, and other data for this study. The DSMC will address any issue that raises questions about data integrity or trial participant safety with the Investigator and study team. Should any major concern arise, the Knight DSMC may recommend corrective action, and determine whether to suspend or terminate the study.

The Knight DSMC evaluates each protocol to determine the risk profile of the trial design. This assessment establishes trial reporting requirements commensurate with risk, and also directs the scope and frequency of Quality Assurance audits. The DSMC may adapt report and audit requirements at any time, if indicated (refer to the Knight DSMP for additional details on reporting and audit frequency). The Investigator will submit trial-specific data reports for the DSMC to assess toxicity and safety data; the report must provide the DSMC with such information as: up-to-date participant accrual; treatment regimen information; current dose level information; AEs and SAEs reported by category; summary of any death on study; unexpected AEs that have been reported; AEs of special or clinical interest; deviations from the approved protocol; that have been reported eligibility exceptions; any inspection, audit, or monitor report; publications and/or developments that may affect scientific validity, subject safety or the ethics of the trial, and a summary of trial status. The study team will provide other information (e.g. scans, laboratory values) upon request.

### 9.2 CLINICAL DATA & SAFETY MONITORING

As part of the Quality Assurance plan and in full agreement with NIH policy that states all clinical trials require monitoring to ensure the safety of study participants and the validity and integrity of the data, monitoring will be a continuous, ongoing and multifaceted process. This includes external review by the DSMC and IRBs, as well as internal data quality control, review and evaluation. Site monitoring visits are central to this process, and will include reporting to appropriate individuals with oversight responsibilities. STUDY MONITORING REQUIREMENTS The Investigator is responsible for ensuring that the study is conducted in accordance with the protocol, Declaration of Helsinki, GCP, and applicable regulatory requirements, and that valid data are entered into the (e)CRFs. To achieve this objective, the monitor's duties are to aid the Investigator and, at the same time, the Sponsor in the maintenance of complete, legible, well organized and easily retrievable data. Monitoring visits will be performed during the study to

ensure that the rights and well-being of human participants are protected, that the reported trial data are accurate, and that the conduct of the trial is in compliance with the protocol, GCP, and applicable regulatory requirements.

Details of monitoring activities, including designation of assigned monitoring entities, scope of monitoring visits, timing, frequency, duration of visits, and visit reporting, will be included in a separate Trial-Specific Monitoring Plan (TSMP).

The Investigator will permit the Sponsor or their designee to monitor the study as frequently as deemed necessary to determine that data recording and protocol adherence are satisfactory. The Investigator agrees that the monitor will be permitted to conduct monitoring visits at appropriate intervals. The Investigator agrees to provide all relevant information and documentation as requested by the monitor, including access to all original study documents and source data, including access to electronic medical records and/or source documents if necessary. The Investigator and his/her staff will be expected to cooperate with the monitor and provide any missing information, whenever possible.

The monitor will conduct source data review and verification as outlined in the TSMP, and following each visit will generate a report summarizing the visit findings.

Regardless of monitoring entity, the OHSU Sponsor-investigator is ultimately, singularly responsible for overseeing every aspect of the design, conduct, and final analysis of this investigation and for governing trial conduct at all participating sites.

If at any time Investigator noncompliance is discovered at OHSU or any participating site, the Sponsor-investigator shall promptly either secure compliance or end the Investigator's participation in the study.

Independent audits may be conducted by the Knight DSMC to verify that the rights and well-being of human participants are protected, that the reported trial data are accurate, that the conduct of the trial is in compliance with the protocol and applicable regulatory requirements, that monitoring practices are adequate and in compliance with the monitoring plan, and that evidence of ongoing investigator oversight is present.

